10.10 PBC Medication

The initiation of PBC medication while on the study will be treated as rescue medication in the analysis. All PBC medication usage during the study will be collected on the Prior and Concomitant medication CRF page and the category will be "PBC Treatment". PBC medication that was ongoing at the time of screening will not be considered as impacting the efficacy analysis. If a subject with ongoing PBC medication at time of screening has a temporary medication interruption during the study and the medication is subsequently resumed, this will not be considered a new PBC medication impacting efficacy. The use of UDCA is required during the study, unless the subject is intolerant to UDCA. Obeticholic acid (OCA), fenofibrate and bezafibrate are also permitted during the study. If a stable dose is maintained throughout the study these may not be considered rescue therapies.

All PBC treatment will be reviewed and assessed for the impact on efficacy. If a subject is identified as having a record that potentially impacts efficacy (i.e., the PBC medication started after randomization), all efficacy data collected following the start date of the medication will be treated as missing data for the analysis of the primary, secondary and exploratory endpoints.

The date of PBC medication initiation is defined as the first date/time of PBC treatment identified as impacting efficacy record in the CRF. For imputation of partial dates refer to Appendix 2. An assessment or event will be defined as prior to PBC medication initiation if the date/time of the assessment or event occurred prior to the date/time of the first PBC medication usage. Otherwise, the event will be considered after PBC medication use. If the assessment of event only has date collected, then prior to PBC medication includes assessments or events that occurred on the day of the first PBC medication usage. Time to PBC medication use will be defined as:

Time to PBC Medication Use = Start Date of PBC Medication - First dose of IMP + 1

The identification of PBC medication impacting on efficacy will be conducted through a blinded medical review prior to the primary analysis.

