12.5.2 Primary Estimand

For the primary efficacy analysis, each setanaxib treatment group (1600 mg and 1200 mg) will be compared with placebo. The primary estimand is to assess the change in ALP (%) over 24 weeks in subjects with PBC, elevated liver stiffness, and intolerance or inadequate response to UDCA.

The intercurrent events of Important protocol deviations impacting efficacy and treatment discontinuation prior to Week 24 for any reason not considered under the Composite Strategy (below) will be handled with a treatment policy strategy (the primary estimand) and the value recorded for the variable of interest is used regardless of whether or not the intercurrent event occurs (ICH E9 R1 addendum). The intercurrent events of starting additional PBC-related medications after randomization and prior to Week 24 or death prior to week 24 will be handled with a composite variable strategy, where efficacy data collected following the intercurrent event will be excluded from the primary analysis. PBC-related medication(s) will be identified through blinded medical review prior to database lock.

Table 6: Definition of Intercurrent Events

Intercurrent Event	Strategy	Comment
Important protocol deviations that impact efficacy	Treatment policy strategy	The occurrence of the intercurrent event is considered irrelevant in defining the treatment effect of interest, the value for the variable of interest is used regardless of whether or not the intercurrent event occurs
Starting additional PBC-related medications after randomization and before Week 24 Death before Week 24	Composite variable strategies	Efficacy data collected after these events will be excluded from the primary analysis.

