12.5.2.2 Sensitivity Analyses

For continuous endpoints to be analyzed using MMRM, no explicit imputation of missing data is needed as the MMRM analysis will be performed on observed cases and implicitly imputes missing data. =

Sensitivity analyses using different ways of handling missing ALP data will be performed for the primary endpoint to assess the impact of missing data and the intercurrent strategy on the primary efficacy results:

- 1. Sensitivity analysis #1 While it is intended that complete data will be recorded at 24 weeks, if there is a significant amount of missing data, the robustness of the primary analysis will be assessed using multiple imputation (Section 12.5.2.2.1)
- 2. Sensitivity analysis #2: If examination of residual plots indicates significant outliers, then ALP data at 24 weeks will additionally be analyzed using a Robust Regression approach after first multiple imputing any missing data (Section 12.5.2.2.2)

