12.5.2.2.1 Sensitivity Analysis #1 - Multiple Imputation for Sensitivity Analysis of Primary Endpoint

If missing data are observed following discontinuation, the MMRM will estimate what would have happened had patients not discontinued, and the treatment effect may be biased. To assess the robustness, a multiple imputation approach will be performed where the relationship between ALP data and time from discontinuation will be modelled within each treatment group separately, and using that relationship, data missing post-discontinuation will be imputed based on data observed post-discontinuation in other patients.

The imputation model will include data from baseline and Weeks 2, 4, 8, 12, and 24 and will impute missing ALP values as follows:

 For subjects who discontinue study treatment and who do not have subsequent ALP measurements, the missing data imputation method will use subjects in the same treatment arm who discontinue study treatment and do have subsequent ALP measurements (defined as

Version Date: 27-June-2024

Sponsor: Calliditas Therapeutics Suisse SA

Protocol No: GSN000350

'retrieved dropouts') allowing for how long prior to each visit the subject discontinued. Therefore, if there is some loss of efficacy post discontinuation of therapy, subjects who discontinue study treatment and have missing data will have data imputed based on such a loss of efficacy.

- For subjects who initiate a new PBC medication, all data collected post the commencement of PBC medication will be treated as missing data in the model.
- In the unlikely event that subjects die before a visit, they will have the largest ALP value, observed across treatment arms, imputed at that visit.

The variables to be used in the analysis are described below together with sample SAS® code [Note the actual variable names may vary in the analysis]:

- TRT = treatment group
- VAL1-VAL5 = log-ALP value at each post-baseline visit for Weeks 2,4,8,12 and 24, respectively

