- WDAW1-WDAW5 = Time from treatment discontinuation at Weeks 2,4,8,12 and 24, respectively. Covariates will be constructed for each scheduled visit up to Week 24 and depending on the time point being imputed, the corresponding covariate will be used in the imputation model. For example, if Week 24 is being imputed the Week 24 covariate below will be used to determine time from treatment discontinuation in the model. Each WDAW covariate takes a value of 0 if a subject is still receiving therapy at that visit and will be fitted as class variables. The value of the covariates will be derived as follows (the visit windows defined in section 10.3 will be applied):
 - WDAW1 (Week 2 Visit): If the subject discontinued treatment prior to Week 2 Visit set to
 1; otherwise set to 0
 - WDAW2 (Week 4 Visit): If the subject discontinued treatment prior to Week 2 Visit set to
 2; if the subject discontinued IMP on or after Week 2 Visit but prior to Week 4 Visit set to
 1; otherwise set to 0
 - WDAW3 (Week 8 Visit): If the subject discontinued treatment prior to Week 2 Visit set to 3; if the subject discontinued IMP on or after Week 2 Visit but prior to Week 4 Visit set to 2; if the subject discontinued treatment on or after Week 4 Visit but prior to Week 8 Visit set to 1; otherwise set to 0
 - WDAW4 (Week 12 Visit): If the subject discontinued treatment prior to Week 2 Visit set to 4; if the subject discontinued treatment on or after Week 2 Visit but prior to Week 4 Visit set to 3; if the subject discontinued treatment on or after Week 4 Visit but prior to Week 8 Visit set to 2; if the subject discontinued treatment on or after Week 8 Visit but prior to Week 12 Visit set to 1; otherwise set to 0
 - O WDAW5 (Week 24 Visit): If the subject discontinued treatment prior to Week 2 Visit set to 5; if the subject discontinued treatment on or after Week 2 Visit but prior to Week 4 Visit set to 4; if the subject discontinued treatment on or after Week 4 Visit but prior to Week 8 Visit set to 3; if the subject discontinued treatment on or after Week 8 Visit but prior to Week 12 Visit set to 2; if the subject discontinued treatment on or after Week 12 Visit but prior to Week 24 Visit set to 1; otherwise set to 0
- WD = binary covariate indicating whether the subject had discontinued from therapy prior to Week 24 Visit
- USUBJID = Subject ID
- VISIT = Visit name
- CHG = Change of log-ALP baseline ratio at each visit
- BASE = log-baseline ALP

Version Date: 27-June-2024

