Note, individual covariate terms for time from treatment discontinuation may be dropped from the model and/or factor levels removed if a particular pattern of missing data is not present when data are unblinded. In particular, if there are subjects present with missing data for a specific level of one of the covariates for time from treatment discontinuation, but there are no matching subjects with data observed for the same level of the same factor in the same treatment arm, the factor level will be grouped with the next highest level to enable the imputation model to be run (for example Week 2 will be grouped with Week 4). This will require running separate MI procedures if the pattern differs by treatment arm.

In the event that the above model fails, the time from treatment discontinuation covariates may be removed as follows

Sponsor: Calliditas Therapeutics Suisse SA

Protocol No: GSN000350

Proc mi data=partial nimpute=1 seed=439384 out=impute minmaxiter=100000; monotone regression; var BASE VAL1-5; by TRT imputation_; run;

Step 3: the MMRM model is applied to the transposed, imputed data. Any subject who dies prior to a visit will have worst case data imputed only at this stage prior to analyzing the data. Baseline ALP will be included as a covariate and will be calculated as the geometric mean of pre-randomization ALP results, as defined in section 10.1 and log-transformed prior to inclusion in the analysis model. The model will also include terms for treatment group, visit, log(baseline) by visit, and visit by treatment group interaction. Subject will be included as a random effect.

An unstructured covariance matrix will be used to model the within-subject correlation of data. The Kenward-Roger's degrees-of-freedom adjustment will be used. Restricted maximum likelihood will be used to obtain parameter estimates. Model assumptions of the MMRM will be assessed using residual plots (such as q-q plots, histograms, box plots, and scatter plots). If the model above does not converge, heterogeneous Toeplitz covariance structure will be used instead of the unstructured covariance matrix. If convergence still does not meet, the Toeplitz structure will be used.

```
proc mixed data=imputed method=reml;
    class TRT USUBJID VISIT;
    model CHG = TRT VISIT BASE BASE*VISIT VISIT*TRT /ddfm=kr;
    repeated VISIT/ sub = USUBJID type = un;
    lsmeans TRT*VISIT /cl pdiff;
    by _imputation_;
    ods output LSMeans=mixlsmean Diffs=mixdiff;
run:
```

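### SAP 12.5.2 calls new PBC medication and death composite events, but for ALP change it only excludes later values; no planned analysis reliably tests that choice or missing at random for the two dose comparisons

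*SAP*

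**What the plan says.** **Label and rule.** SAP 12.5.2 and Table 6 place two events, new PBC medication and death before Week 24, under a composite strategy. They state that these events "will be handled with a composite variable strategy, where efficacy data collected following the intercurrent event will be excluded from the primary analysis". SAP 10.10 gives the data rule for new PBC medication: "all efficacy data collected following the start date of the medication will be treated as missing data for the analysis of the primary" and the other efficacy endpoints. SAP 12.5.2.1 repeats this for ALP. Protocol 8.4.1.1 describes the same exclusion without calling it composite.

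**Primary model.** SAP 12.5.2.2 says that "no explicit imputation of missing data is needed as the MMRM analysis will be performed on observed cases and implicitly imputes missing data".

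**Sensitivity analyses.** Protocol 8.4.1.3 commits the SAP to testing the intercurrent-event strategy and the MAR assumption.
- Sensitivity #1 (SAP 12.5.2.2.1) imputes from patients in the same arm who stopped treatment but still have ALP values, by time since stopping. SAP 12.5.2.2 plans it "if there is a significant amount of missing data", and Step 4 adds that there must be enough such patients. For new PBC medication, "all data collected post the commencement of PBC medication will be treated as missing data in the model". For patients who die, "they will have the largest ALP value, observed across treatment arms, imputed at that visit".
- Sensitivity #2 (robust regression) is planned if residual plots show outliers or non-normality. It states the same MAR assumption as the MMRM.
- SAP 10.18 and Table 7 list the imputation analysis of the primary endpoint with no condition attached.
- SAP 12.5.2.3 repeats the primary model on the Per Protocol Set (PPS).

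**The concern.** A composite strategy makes the event part of the outcome: the patient receives a value or status because the event happened. The SAP does this for the responder endpoints in 12.5.4.1, where a patient who starts PBC medication counts as a non-responder. It does not do so for change in ALP. A reader of the study report would take the primary result as one in which new PBC medication counts against the patient, when it estimates ALP as if the new medication had not been started.

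Death has two rules. In the primary analysis, excluding later data does nothing, because there are none. In Sensitivity #1 the worst observed value is assigned.

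Also at stake is the protocol's promise. If Sensitivity #1 does not run or is cut back, the two comparisons that carry the Hochberg test have no planned analysis showing how far missing or excluded Week 24 values would have to depart from MAR to change the conclusion.

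**Working it through.** **1. What is estimated for new PBC medication.** Later ALP is set to missing (SAP 10.10, 12.5.2.1) and the observed-case MMRM predicts it (12.5.2.2). SAP 12.5.2.2.1 itself says that, where data are missing after discontinuation, the MMRM estimates the outcome as if patients had not discontinued. That is a hypothetical-type target.

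**2. What each planned analysis changes.**
- *Sensitivity #2*: same exclusion, same MAR assumption.
- *Sensitivity #1*: same exclusion, different prediction. "Each WDAW covariate takes a value of 0 if a subject is still receiving therapy at that visit". Under Protocol 6.7, starting PBC treatment leads to IMP discontinuation, so these covariates do apply to starters. But there are two gates (12.5.2.2; Step 4) and two fallbacks. Step 2 says "In the event that the above model fails, the time from treatment discontinuation covariates may be removed as follows", and Step 4 allows fewer covariates or a simpler method. Without those covariates it is imputation under essentially the MMRM's own assumption.
- *PPS repeat*: starters drop out only if classed as prohibited-medication deviations (SAP 9.6.4). Protocol 4.4.1 calls introducing standard PBC treatment allowed, so that classing is uncertain. Either way, the exclusion rule is unchanged and MAR is not tested.
- *SAP 12.5.3.2*: extends the imputation to combined-dose ALP, not to the two separate dose comparisons.

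**3. Illustration: a true composite.** Design means are reductions of 25% and 2.5% (Protocol 8.3; SAP 8.1), with 22 enrolled per arm.
- Design effect: log(0.75/0.975) = -0.2624, that is -23.1%. The primary handling keeps this target if excluded values would have followed the MAR prediction.
- Assume that k_s setanaxib and k_p placebo patients start new medication and receive v times baseline. The composite effect is [(1 - k_s/22) log 0.75 + (k_s/22) log v] - [(1 - k_p/22) log 0.975 + (k_p/22) log v].

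| Starters (setanaxib, placebo) | v = 1.00 | v = 1.25 |
|---|---|---|
| 1, 0 | -22.1% | -21.3% |
| 3, 0 | -20.0% | -17.5% |
| 0, 3 | -23.3% | -25.6% |
| 3, 3 | -20.3% | -20.3% |

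The effect can move either way. The counts and v are assumptions; the documents give neither.

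**4. Illustration: tipping point.** The planned SDs are 19% (setanaxib) and 24% (placebo), in the order of the sample-size text. Log SD = sqrt(log(1 + CV^2)). For setanaxib, CV = 19/75 gives 0.249; for placebo, CV = 24/97.5 gives 0.243. Missing values are imputed under MAR, a shift d is added to the imputed setanaxib log values, and results are pooled by Rubin's rules with small-sample degrees of freedom. The pooled effect is -0.2624 + (m/22)d, where m is the number missing per arm.

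| Missing per arm | One-sided p under MAR | p passes 0.0125 | p passes 0.025 |
|---|---|---|---|
| 6 of 22 | 0.0035 | about 18% above prediction | about 30% above |
| 3 of 22 | 0.0014 | about 53% above | about 75% above |

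Under Hochberg, 0.0125 is needed only if the other dose fails. In the first row the 30% point is full reversion to the placebo mean (0.975/0.75 = 1.30), where the effect is -0.2624 x 16/22 = -0.1908, or -17.4%.

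One caveat applies to the SDs. The plan's power pair (88.2% and 68.3%) reproduces with the two SDs exchanged (88.3% and 68.8%) but not in sentence order (84.7% and 71.5%). Exchanged, the log SDs are 0.312 and 0.193, and the summed variance is 0.135 instead of 0.121, so the tipping points would be somewhat lower.

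**5. Step 4 sample code.** `proc mianalyze` reads `mixlsmean` by visit only, so it pools the arm means as if they were one estimate. At the design values this gives (2 log 0.75 + log 0.975)/3 = -0.2002, or -18.1%: a grand mean change from baseline, not the -23.1% treatment effect that the text promises. Step 3 already outputs the differences as `mixdiff`.

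**The case against.** The operation is clear and consistent across both documents, so a new label changes no dataset, model or p-value. That is true of the primary analysis, but the label decides what the result is said to mean. The SAP calls death unlikely, and the missing rule matters only if one occurs.

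The trial is an exploratory Phase 2b study, and the choice among departure-from-MAR methods is partly a matter of preference. Any such method would do. The need for one comes from Protocol 8.4.1.3, and the primary endpoint is formally tested with type I error control.

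The gate on Sensitivity #1 has some logic: with 3 of 22 missing the result is hard to overturn, and with 6 of 22 the analysis would probably be triggered. What remains is substantial missingness with too few retrieved dropouts, or the fallback without covariates. SAP 10.18 and Table 7 state no gate, so the SAP is inconsistent rather than plainly conditional. The protocol also asks for every effort to obtain the Week 24 visit.

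Three stronger readings are tempting, and the documents support none of them.
- *The exclusion favours setanaxib.* No event rates are given, and events mainly on placebo would move a composite the other way.
- *Table 7 is wrong to label Sensitivity #1 as MAR.* Imputing from same-arm patients by time since stopping is MAR conditional on discontinuation time. The label is incomplete, not false.
- *Power is lost.* Nothing here shows that.

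**Conclusion.** The point holds as a mismatch between label and rule, together with a protocol commitment that the SAP does not secure. For change in ALP, new PBC medication is handled by a hypothetical-type strategy, and death has no rule in the primary analysis and a different one in Sensitivity #1. No planned analysis of the two dose comparisons changes the exclusion rule. Only the full form of Sensitivity #1 relaxes the MMRM's simple MAR assumption, and the SAP does not guarantee that form.

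The practical size is unknown. The composite range of -17.5% to -25.6% rests on assumed counts of up to 3 of 22 starters in an arm and assumed values of 1.00 to 1.25 times baseline. The tipping points rest on the planned means and SDs. They show that robustness depends on how many Week 24 values are retrieved, which is why the check should not be optional. The sample-code slip is minor and separate, because the text around it is right.

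**What to change.** 1. In SAP 12.5.2 and Table 6, relabel new PBC medication as hypothetical, or define the composite value that enters the primary ALP variable. State one rule for death and use it in the primary and sensitivity analyses.
2. Add one unconditional departure-from-MAR analysis of Week 24 ALP for each dose versus placebo, for example a delta-adjusted tipping point. It should also cover values excluded after new PBC medication. Keep Sensitivity #1 where feasible, reconcile 10.18 and Table 7 with 12.5.2.2 and Step 4 on whether it is conditional, and state in Table 7 that its assumption is MAR given discontinuation time.
3. In the Step 4 sample code, pool `mixdiff` by same-visit treatment contrast instead of `mixlsmean` by visit.

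The cost is SAP wording and one extra multiple-imputation run on existing data, with no new data collection.

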12.5.2.1 Primary Analysis

Change in ALP at each scheduled timepoint up to Week 24 will be explored via tabulation and graphs for the FAS. Counts for the number of subjects that have a ≥15%, ≥30%, ≥40%, ≥50% and ≥70% reductions in ALP from baseline will be presented (these counts will be cumulative i.e a subject with ≥30% reduction at Week 24 will be counted in both ≥15% and ≥30% categories. Summary statistics for each schedule timepoints will be presented. These will include the geometric mean, geometric mean +/- geometric

Version Date: 27-June-2024

Sponsor: Calliditas Therapeutics Suisse SA

Protocol No: GSN000350

standard deviation, median, minimum, maximum. Baseline will be summarized in two ways – including all baseline data and baseline recalculated for subjects with evaluable Week 24 results (i.e. the subset of patients who have both baseline and week 24 ALP results).

In order to summarize % change at each scheduled timepoint, the ratio of ALP to baseline will be calculate for each scheduled timepoint and a logarithmic transformation applied. The mean and mean +/- standard deviation and mean +/- standard error of the log ratios will be calculated. The results will be backtransformed to get the geometric mean ratio (+/- geometric standard deviation and +/- geometric SE).

These results will be converted to the % scale and plotted as a line graph for each treatment group. ALP values after initiation of PBC-related medication will be treated as missing values at the analysis visit following initiation of the medication.

For the primary analysis, the ratio of ALP at week 24 to baseline will be log-transformed, as will ALP data from other timepoints used in the model. This will be analyzed using a Mixed Model Repeated Measures (MMRM) analysis based on the FAS and incorporating ALP data from baseline, weeks 2,4,8,12 and 24. Baseline ALP will be included as a covariate and will be calculated as the geometric mean of prerandomization ALP results, as defined in section 10.1 and log-transformed prior to inclusion in the analysis model. The model will also include terms for treatment group, visit, log(baseline) by visit, and visit by treatment group interaction. Subject will be included as a random effect.

the Mixed Model Repeated Measures (MMRM) model can be mathematically represented as follows:

$$Y_{ij} = \beta_0 + \beta_1$$
 · Treatment $_i + \beta_2$ · Visit $_j + \beta_3$ · (log (Baseline ALP $_{ij}$)) + β_4 · (log (Baseline ALP $_{ij}$ × Visit $_i$) + β_5 (Treatment $_i$ × Visit $_i$) + b_i + ϵ_{ij}

- Y_{ii} is the observed response (log-transformed ratio of ALP at visit j (up to Week 24) to baseline).
- β_0 is the overall intercept.
- β_1 is the effect of treatment group *i*.
- β_2 is the effect of visit j.
- β_3 is the effect of baseline ALP.
- β_4 is the interaction between log-transformed baseline and visit.
- β_5 is the interaction between treatment and visit.
- b_{ijk} represents the random effect for the subject k.
- ϵ_{ii} is the residual error term.

An unstructured covariance matrix will be used to model the within-subject correlation of data. The Kenward-Roger's degrees-of-freedom adjustment will be used. Restricted maximum likelihood will be used to obtain parameter estimates.

Assessment of model assumptions:

Model assumptions of the MMRM will be assessed. Where the residual errors ϵ_{ij} are assumed to be independent and identically distributed with constant variance; the random effects b_{ijk} are assumed to be normally distributed with mean zero.

- 1. The assumption of linearity (linear relationship between log-transformed ratio of ALP with independent variables) and homoscedasticity will be checked using residual plots.
- 2. The assumption for normality of residuals will be checked using QQ plots.

Assessment of model convergence:

Version Date: 27-June-2024

Sponsor: Calliditas Therapeutics Suisse SA

Protocol No: GSN000350

- If the model using unstructured covariance matrix does not converge, heterogeneous Toeplitz covariance structure will be used instead of the unstructured covariance matrix. If the model still fails to converge, the Toeplitz structure will be used.
- If the above method does not lead to convergence of the model, consideration will be given to increasing the maximum number of iterations, changing the optimization technique, or adjusting the convergence criteria to promote model convergence.
- If the above optimization still fails to make the model converge, the following models (removing baseline * visit interaction term and removing the baseline term) will be used until the model converges.

$$Y_{ij} = \beta_0 + \beta_1 \cdot \text{ Treatment }_i + \beta_2 \cdot \text{ Visit }_j + \beta_3 \cdot \left(\log\left(\text{ Baseline ALP }_{ij}\right)\right) + \beta_4\left(\text{ Treatment }_i \times \text{ Visit }_j\right) + b_i + \epsilon_{ij}$$

$$Y_{ij} = \beta_0 + \beta_1 \cdot \text{ Treatment }_i + \beta_2 \cdot \text{ Visit }_j + \beta_3 \cdot \left(\text{ Treatment }_i \times \text{ Visit }_j\right) + b_i + \epsilon_{ij}$$

Data presentation:

The least squares means will be estimated by visit along with the associated 95% CI. Geometric least squares mean values will be obtained by exponentiating the least squares means.

The treatment effect will be expressed as the % change in ALP for each setanaxib dose versus placebo, derived from the geometric least squares mean ratios estimated at Week 24 (and scheduled timepoints up to Week 24) interacted with each treatment arm. The 95% CI and 1-sided p-value will be presented.

To aid interpretation, corresponding estimated absolute change from baseline for each arm and the estimate absolute change versus placebo and 95% CIs will be estimated from the ratios.

